### **7.3 Passively Collected Data**

In addition to surveys, patient and nurse practitioner data will be recorded through the web interfaces of HN-STAR. In addition, NPs will document clinic notes as part of routine care. These data will be used to inform feasibility of HN-STAR and contribute to power calculations for the future multi-site randomized controlled trial.

**7.3.1** For all visits at MSK, preceding the patient visit, the NP will verify the Automated Treatment Checklist. When the NP makes any changes to imported data and verifies the final Treatment Checklist, these data will be collected. These data will inform the accuracy of the automatically generated treatment summary and the time required to verify the information.

**7.3.2** For all visits at HH, preceding the patient visit, the NP will complete the Manual Treatment Checklist. Data will be collected regarding the time required to complete the checklist.

**7.3.3** All patients will complete the Survivor Self-Assessment before their clinic visit. HN-STAR will record the amount of time taken, the items skipped, and the proportion of the Self-Assessment completed.

**7.3.4** As part of routine care, the NP will record topics addressed and actions taken in the clinic note for each visit. Clinic notes regarding the identification and management of late effects will be abstracted.

### **7.4 Preliminary metrics for future trial**

Abstracted clinic note data and HN-STAR data will inform feasibility of data collection and assess preliminary outcomes for Aim 2.

**7.4.1** Clinic note data will be used as part of a pretest-posttest design, described in further detail in the Biostatistics section 11.3. At each clinic visit, the NP will record actions from the visit, including referrals, prescriptions, and other management plans in the clinic note as part of routine care. The RSA at each site will retrieve data regarding late effects identified and addressed in the year preceding the study visit and during the study visit, to assess changes before and after the HN-STAR intervention. The RSA will also assess

oncologic surveillance occurring in the year preceding the study visit and during the study visit from the medical record. RSAs will use the Medical Record Data Abstraction Form (Appendix H).

**7.4.2** The receipt of routine preventive care, including cancer screening tobacco cessation, immunizations, and routine general testing, is not routinely collected in the clinic note and will instead be collected from HN-STAR. We will only collect these outcomes once (before the HN-STAR visit), and they will not serve as outcomes for the pretest-posttest study.

## 7.5 Columbia University as data analysis site

All survey data collected via WebCore will be analyzed at MSK, as will the NP interview data. Usability data and interview data with patients and the NP from Aim 1: Part 1 in the MSK survivorship clinic will be analyzed by [name] at Columbia University. All of the data will be identified by a unique participant identifier and the date of assessment. Data will be stored at MSK and shared with [name] using the MSK secure file-transfer system, ShareBox.

## 8.0 TOXICITIES/SIDE EFFECTS

We do not anticipate any toxicities or side effects from participating in this study. Although unlikely, there is a chance patients may experience emotional distress while discussing their symptoms or health condition. In any case of participant distress, we will encourage the patient to discuss his or her concerns with the NP, or other members of the clinical team. Referral to appropriate staff will be facilitated if necessary including social work, psychology or psychiatry.

## 9.0 PRIMARY OUTCOMES

The following table shows the timing of each assessment in the study. The content and sources for each assessment are described in Section 7.1, 7.2, 7.3, and 7.4 above.

*Figure 4. Outcome collection*

Assessment	Source	Timing (including end of data collection window)
Aim 1: Part 1: Component pilot testing		
Survivor Post-Assessment Survey	Patient	Upon completion of Survivor Self-Assessment
Survivor Post-Assessment Interview	Patient	Upon completion of Survivor Post-Assessment Survey
Survivor Post-Visit Survey	Patient	After clinic visit, and after receiving Survivorship Care Plan
Survivor Post-Visit Interview	Patient	Upon completion of Survivor Post-Visit Survey
Nurse Practitioner Post-Visit Survey	NP	Following each clinic visit, within 2 days of clinic visit
Nurse Practitioner Interview	NP	After 10 patients have completed Aim 1: Part 1, within 1 month of last patient completing Aim 1: Part 1
Aim 1: Part 2: Feasibility in Clinical Practice		

Assessment	Source	Timing (including end of data collection window)
Survivor Post-Assessment Survey	Patient	Upon completion of Survivor Self-Assessment, before the clinic visit

**Figure 4 continued. Outcome collection**

Assessment	Source	Timing (including end of data collection window)
Survivor Post-Visit Survey	Patient	Following clinic visit, before leaving clinic
Primary Care Provider Survey	PCP	At least one week after being mailed Survivorship Care Plan, within a month of enrollment into study
Passively collected feasibility metrics	HN-STAR	Immediate concurrent data collection via Webcore
Nurse Practitioner Interview	NP	After 30 patients have completed Aim 1: Part 2 at MSK and 15 patients have completed Aim 1: Part 2 at HH, within 1 month of last patient completing Aim 1: Part 2 at the respective site
Survivor Follow-up Interview	Patient	Six months after the clinic visit
Preliminary metrics for future trial (Aim 2)		
Oncologic metrics: Late effects identified and addressed, receipt of head and neck surveillance and appropriate follow-up (e.g. dental exam for those who underwent radiation therapy)	Clinic notes, prescriptions or referrals	Abstracted from any time in the year before the visit (pretest) and in the note pertaining to the clinic visit (posttest)
Non-oncologic metrics: Receipt of routine preventive care (e.g., cancer screening, tobacco cessation)	Survivor Self-Assessment	After completion of the Survivor Self-Assessment

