- >50% of survivors rate the Survivorship Care Plan positively. For survivors, item response will be defined as positive if they report that they strongly agree or agree with the items #25-29 on the Survivor Post-Visit Survey (Appendix E). A survivor will be considered as having a positive overall rating of the Survivorship Care Plan if at least 3 of the five responses are positive.>50% of primary care providers rate the Survivorship Care Plan positively. For primary care providers, item response will be defined as positive if they report that they strongly agree or agree on items #2, 4-6, 8-14. Because of the wording, for items #3 and 7 responses of disagree or strongly disagree will be defined as positive on the Primary Care Provider Survey (Appendix G). If at least 7 of 13 items are positive, we will consider this a positive overall rating to the survivorship care plan.
- If any component does not meet all criteria, we will consider further adapting the component as needed and testing them further in a future protocol.

We will use qualitative data from study interviews to supplement our understanding of usability issues for both the NP and survivors in Aim 1: Part 1. We will use grounded theory to identify salient themes regarding the usability of the Survivor Self-Assessment, the Automated Treatment Checklist, the Interactive Discussion Guide, and the Survivorship Care Plan from the perspectives of both the survivors and the NP.

**11.3 Analysis Aim 2: Collection of preliminary metrics of health care actions.** As described in Section 9.0, relevant metrics for Aim 2 are both oncologic and non-oncologic. We will collect oncologic metrics from any clinic notes that appear in the patient's chart in the year preceding the HN-STAR visit and for the HN-STAR visit itself. Non-oncologic metrics will be collected only from the HN-STAR patient assessment completed before the HN-STAR visit. We will use descriptive statistics to report receipt of oncologic and non-oncologic care.

Also as described in Section 9.0 and listed completely in Appendix H, oncologic outcomes include late effects (symptoms) **identified** and **addressed**, receipt of head and neck surveillance and appropriate follow-up (e.g. dental exam for those who underwent radiation therapy). Non-oncologic outcomes include receipt of recommended routine preventive care (e.g., cancer screening, tobacco cessation).

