**11.3.1 Oncologic outcomes.** We will only investigate late effects that we assess in HN-STAR. (If usability testing identifies additional late effects we did not target in our Survivor Self-Assessment, we will add them to the Survivor Self-Assessment for Aim 1: Part 2 and include them in Appendix H.) For each late effect, we will consider it identified if it was mentioned in a clinic note, and we will consider it addressed if there was a referral,

recommendation, education, or explicit acknowledgement of inaction. (Inaction may be appropriate, because in some cases, when symptoms are persistent and intractable, no intervention may be recommended.) For each patient, we will first count the number of late effects identified. We will then calculate the proportion of identified late effects that are addressed.

We will use descriptive statistics to report each element of oncologic care listed in Appendix H (i.e. smoking cessation, dental exam, blood work for thyroid studies, endoscopic exam, and head and neck physical exam). Each patient may not require every element of follow-up, depending on their primary tumor site or treatment received. We will use the number of recommended elements of care as the denominator, and we will calculate the proportion of these elements that are performed.

**11.3.2 Non-oncologic outcomes.** The non-oncologic outcomes in HN-STAR are collected only once. They include cancer screening, vaccination, and other preventive care elements that are explicitly collected in the Survivor Self-Assessment. Only some of these elements will be recommended for each patient, depending on their age, sex, and behaviors. We will calculate the proportion of recommended elements of non-oncologic care that are performed per patient. In addition, for each element of non-oncologic care, we will calculate the proportion of patients who receive it as recommended.

Findings from Aim 2 will inform whether these metrics can be collected from the EMR and HN-STAR. In addition, they will inform the statistical analysis for the future trial. For oncologic metrics only (Section 9.0, Figure 4), we will calculate the difference before HN-STAR use and after. Differences in oncologic metrics will be used in the power calculation for the proposed randomized trial. Non-oncologic metrics will be reported descriptively to inform the feasibility of collecting these data from self-report.

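### Aim 2 compares a year of prior clinic notes with one HN-STAR visit note, so the before-after difference meant for the future power calculation depends partly on how many prior notes a patient has

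*Combined protocol and SAP*

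**What the plan says.** Three places give the same two windows.

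- Section 9.0, Figure 4 (continued), oncologic metrics: "Abstracted from any time in the year before the visit (pretest) and in the note pertaining to the clinic visit (posttest").
- Section 7.4.1: the research assistant retrieves "late effects identified and addressed in the year preceding the study visit and during the study visit". For surveillance it is "oncologic surveillance occurring in the year preceding the study visit and during the study visit from the medical record".
- Section 11.3: "We will collect oncologic metrics from any clinic notes that appear in the patient's chart in the year preceding the HN-STAR visit", and from the HN-STAR visit itself.

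Section 4.2 (Design) confirms that HN-STAR is used for one routine visit per patient, so the posttest is one note.

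The scoring rule is in Section 11.3.1. For each late effect, "we will consider it identified if it was mentioned in a clinic note". Then, "For each patient, we will first count the number of late effects identified", followed by the proportion of identified late effects that were addressed. The closing paragraph of Section 11.3.2 says that, for oncologic metrics, "we will calculate the difference before HN-STAR use and after", and adds: "Differences in oncologic metrics will be used in the power calculation for the proposed randomized trial".

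The text supplied does not match the study visit to a single prior visit, scale by note or visit, restrict the type of prior note, or say how a patient with no prior note is scored. Appendix H, the abstraction form, is listed but not shown.

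**The concern.** The two sides of the contrast give different opportunity for a mention. Before HN-STAR, a late effect needs to appear only once in a year of notes. With HN-STAR, it must appear in one particular note. The difference therefore mixes the effect of the tool with the number of prior notes, and it can differ from zero when the tool has no effect.

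Section 4.2 presents this contrast as early insight into change after HN-STAR, and Section 11.3.2 commits it to the power calculation of the randomized trial. Section 3.0 names changes in the numbers of late effects identified and managed as that trial's primary outcomes, and gives informing its sample size as a purpose of the present study. A distorted difference would feed directly into that planning.

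Surveillance has the same mismatch. The protocol's own example in Section 4.2.3 is a yearly thyroid test after neck radiation. Such a test can count in the prior year and have no reason to recur at the study visit, which would look like a fall.

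**Working it through.** **Figures in the plan.** There is nothing to reproduce. The study states no alpha, power, effect size or SD, and Section 11.1 says that it is not powered for formal hypotheses. The Aim 2 sample is 30 + 15 = 45.

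**Step 1: what follows from the definitions alone.** Let S1, ..., Sm be the sets of late effects mentioned in a patient's m prior notes, and T the set in the HN-STAR note.

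- Planned difference: |T| - |S1 ∪ ... ∪ Sm|.
- The union is at least as large as any single Sj. For m ≥ 2 the planned difference is therefore ≤ |T| - |Sj| for every j. Equality with a given note holds only if the other notes add no new late effect.
- For m = 1 the two differences coincide.
- For m = 0 the result depends on a scoring rule that the plan does not give. Only scoring the pretest as zero pushes the difference upward.

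**Step 2: illustration.** All inputs here are assumptions: 10 late effects per patient, and a chance that one note mentions a given effect of 0.40 in usual care and 0.70 with HN-STAR. The one-note difference is 10 × (0.70 - 0.40) = +3.0.

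Pretest count = 10 × [1 - P(m)], where P(m) is the chance that none of m notes mentions the effect. With independent notes, P(m) = 0.60^m. With between-note correlation ρ (beta-binomial), a = 0.40(1-ρ)/ρ, b = 0.60(1-ρ)/ρ and P(m) = B(a, b+m)/B(a, b). For m = 2 this reduces to 0.36 + 0.24ρ. At ρ = 0.6, for example, P = 0.504 and the pretest count is 4.96.

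| | ρ = 0 | 0.6 | 0.8 | 0.9 |
|---|---|---|---|---|
| Pretest, 2 notes | 6.40 | 4.96 | 4.48 | 4.24 |
| Difference, posttest 7.0 | +0.60 | +2.04 | +2.52 | +2.76 |
| Difference if HN-STAR does nothing, posttest 4.0 | -2.40 | -0.96 | -0.48 | -0.24 |
| Pretest, 4 notes | 8.70 | 5.79 | 4.89 | 4.44 |
| Difference, posttest 7.0 | -1.70 | +1.21 | +2.11 | +2.56 |

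At ρ = 1 the distortion disappears.

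**Step 3: patients with no prior note.** Take an assumed mix of 5, 10, 15, 10 and 5 patients with 0, 1, 2, 3 and 4 notes.

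- Zero-note patients scored as zero: each contributes +7.0. At ρ = 0 the total is 5×7.0 + 10×3.0 + 15×0.60 + 10×(-0.84) + 5×(-1.70) ≈ 57.1, and 57.1/45 = +1.27. At ρ = 0.6 and 0.9 the means are +2.60 and +3.24.
- Zero-note patients left out (40 remain): +0.55, +2.05 and +2.76.

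A second mix of 10, 20, 10 and 5 patients with 0, 1, 2 and 3 notes gives +2.93, +3.51 and +3.80 with zeros, and +1.77, +2.52 and +2.88 without. The mean exceeds +3.0 only when zero-note patients are present and scored as zero.

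**Step 4: proportion addressed.** Numerator and denominator both change when notes are pooled, and the plan does not say how notes are combined. The direction is not fixed.

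**The case against.** The strongest case against is about weight. Section 3.0 calls these problems chronic, and Section 11.3.1 allows for persistent and intractable ones. That points to repeated mention, where the loss is modest: at correlation 0.9 the assumed +3.0 becomes +2.76 with two notes and +2.56 with four. Aim 2 chiefly asks whether the metrics can be collected, nothing is formally tested, and no Section 11.2 criterion uses the difference. A full-year baseline may be deliberate, and Appendix H might already record by note. All of this limits the size of the problem. None of it makes the two windows alike, and the wording in Sections 7.4.1, 9.0 and 11.3 would still need to change.

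Three stronger readings are tempting and are not supported.

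- *The contrast is biased in a known net direction, or may overstate the benefit.* An upward shift needs patients with no note of any kind in the year, scored as zero. The documents suggest neither, and Section 11.3 draws on any clinic note in the chart.
- *The future trial will be missized by a given factor.* Squaring 3.0/0.60 gives 25, and squaring 3.0/2.76 gives 1.2. Such factors hold the SD fixed and take a one-note contrast as the target. Section 3.0 states no window for the future outcome; with a prior-year baseline there, the planned contrast could be the relevant one.
- *The feasibility conclusions are compromised.* They do not use this difference.

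The matched contrast is not clean either. A prior note may omit settled problems (the discussion guide excerpt in Figure 3 has an option for this) or come from another clinician. In the illustration, omitting 2 of the 10 effects gives a pretest of 0.40 × 8 = 3.2 and a difference of +3.8. It should therefore be added beside the full-year contrast, not replace it.

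**Conclusion.** The point holds as a structural mismatch that should be fixed. With two or more prior notes, the planned difference in late effects identified is at most the one-note difference, and it can be negative with no HN-STAR effect. That rests only on the plan's definitions, unless Appendix H sets a per-note rule that the text does not mention.

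Its practical size and net direction over the 45 patients are undetermined. They depend on the number of prior notes, the mention rate per note and the between-note correlation, none of which the documents give. On the assumed inputs, two prior notes turn +3.0 into anything from +0.60 to +2.76. Surveillance has the same year-against-visit mismatch, subject to Appendix H. The consequence is limited to the preliminary effect estimate and the future power calculation.

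**What to change.** Amend Sections 7.4.1, 9.0 (Figure 4) and 11.3 as follows.

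1. Before abstraction, define an index note: the most recent routine head and neck follow-up note in the prior year. For each late effect, record whether the index note identified it and addressed it, separately from the rest of the year, unless Appendix H already records by note. Note date and clinic type alone would not show this.
2. Report the number of prior-year notes per patient. Treat patients with no prior note as missing from the difference, not as zero, and report how many there are.
3. Keep the full-year contrast and add index note against HN-STAR note. Use for the power calculation the one whose baseline window matches the future trial's outcome definition, with the other as a sensitivity range. State that the full-year contrast tends to understate a per-visit change. State also that the matched contrast is noisier and may favour HN-STAR if the prior note omits settled chronic problems or comes from another clinician.
4. Report prior-year surveillance descriptively. Compute no before-after difference for it unless both periods are scored by one common rule.

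Cost: one extra abstraction column across the listed late effects (none if Appendix H is organised by note), wording in three places and one extra contrast. Table 1 lists more than 20 symptoms, so the column is real work, but it uses notes that are being read anyway. Adding it after abstraction would mean a second pass through the charts.

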## 10.0 CRITERIA FOR REMOVAL FROM STUDY

In the unlikely event that researchers or the NP observe acute individual distress during the interviews or clinic visit, they will ask participants whether they wish to continue. Researchers will conclude the interview upon participant request. The patient may voluntarily discontinue participation in the study at any time.

## 11.0 BIOSTATISTICS

**11.1 Sample size.** This feasibility study is not powered to test formal hypotheses. Instead, it will provide feedback regarding the HN-STAR process. We will enroll 10 patients in Aim 1: Part 1. In Aim 1: Part 2, we will enroll 45 additional patients: 30 from MSK and 15 from HH. The MSK clinic sees over 20 patients per month, ensuring that enrollment is attainable. The HH clinic sees approximately 8 patients per month. We anticipate that enrolling 45 patients will not take longer than 6 months. Enrolling PCPs may be more difficult; we anticipate that not all 45 PCPs will complete the Primary Care Provider Survey. Part of our feasibility study is to test whether this method of recruitment and level of incentives will be adequate to recruit PCPs in a future study, and the level of participation will inform this feasibility outcome. Both NPs are integrally involved in implementing HN-STAR in their clinics.

### 11.2 Analysis Aim 1: Parts 1 and 2

The structured survey questions (asked of survivors, NPs, and PCPs in Aim 1: Parts 1 and 2) will be summarized using descriptive statistics. Quantitative outcomes will include survivors' rates of completion of the self-assessment, survey completion rates for survivor, NP, and Primary Care Provider Surveys in the feasibility study. The number of questions to answer is different between surveys and even between respondents, based on skip patterns built into the electronic survey platform. Each survey will be considered complete if at least 75% of questions that are asked are answered. WebCore will automatically capture the percentage of questions that are answered for each survey administered. We will also look at survivor responses by race and ethnicity. Other quantitative outcomes include the median time survivors required to complete the self-assessment, the accuracy of the automated treatment summary (verified against the EMR), the time required for NP verification of the treatment summary, and the length of HN-STAR visits.

Each component of HN-STAR will be evaluated individually for feasibility. We will consider the Survivor Self-Assessment feasible for subsequent effectiveness testing if the following criteria are met:

- >75% survivors completed >75% of self-assessment. The survivor self-assessment has multiple components that include a total of 47 items for men and 49 items for women. We will only include items that are asked of every participant (i.e. no sub questions) for this metric. We will consider 75% of the self-assessment complete if 36 items (for men) and 37 items (for women) are completed.
- The mean proportion of assessment completed >75%.
- The median time to complete self-assessment <15 minutes.
- >50% of survivors rate the Self-Assessment visit positively on the Survivor Post Assessment Survey (Appendix D). For items #13, a response of "No" is positive, for item #14, a response of "yes" is positive, for item #15, a response of "Just right" is positive, and for items 16-18, a response of "Agree" or "Strongly agree" is positive. We will consider a positive overall rating if >50% of responses are positive.

We will consider the Automated Treatment Checklist feasible if the following criteria are met:

- >90% of the treatment summaries were deemed accurate .
- The median time to verify the summary <20 minutes.

We will consider the Manual Treatment Checklist feasible if the following criteria are met:

- The median time to complete <30 minutes. (In practice, survivorship care plans typically take an hour or more to complete.)

The Interactive Discussion Guide will be considered feasible if the following criteria are met:

- >75% of discussion guides did not miss relevant information. We will determine whether relevant information was covered using item #6 from the Nurse Practitioner Survey (Appendix F) for this metric. Responses of "Agree" or "Strongly agree" to the item, "the discussion guide missed important information about the patient will be measured as missing relevant information.
- >50% of survivors rate the survivorship visit positively on the Survivor Post Assessment Survey (Appendix E). For items #1-8, a response of "Agree" or "Strongly agree" is positive. We will consider a positive overall rating if >50% of responses are positive.
- The median visit time <50 minutes (current visit time average is 40 minutes).

The Survivorship Care Plan will be deemed feasible if the following criteria are met:

- >50% of survivors rate the Survivorship Care Plan positively. For survivors, item response will be defined as positive if they report that they strongly agree or agree with the items #25-29 on the Survivor Post-Visit Survey (Appendix E). A survivor will be considered as having a positive overall rating of the Survivorship Care Plan if at least 3 of the five responses are positive.>50% of primary care providers rate the Survivorship Care Plan positively. For primary care providers, item response will be defined as positive if they report that they strongly agree or agree on items #2, 4-6, 8-14. Because of the wording, for items #3 and 7 responses of disagree or strongly disagree will be defined as positive on the Primary Care Provider Survey (Appendix G). If at least 7 of 13 items are positive, we will consider this a positive overall rating to the survivorship care plan.
- If any component does not meet all criteria, we will consider further adapting the component as needed and testing them further in a future protocol.

We will use qualitative data from study interviews to supplement our understanding of usability issues for both the NP and survivors in Aim 1: Part 1. We will use grounded theory to identify salient themes regarding the usability of the Survivor Self-Assessment, the Automated Treatment Checklist, the Interactive Discussion Guide, and the Survivorship Care Plan from the perspectives of both the survivors and the NP.

**11.3 Analysis Aim 2: Collection of preliminary metrics of health care actions.** As described in Section 9.0, relevant metrics for Aim 2 are both oncologic and non-oncologic. We will collect oncologic metrics from any clinic notes that appear in the patient's chart in the year preceding the HN-STAR visit and for the HN-STAR visit itself. Non-oncologic metrics will be collected only from the HN-STAR patient assessment completed before the HN-STAR visit. We will use descriptive statistics to report receipt of oncologic and non-oncologic care.

Also as described in Section 9.0 and listed completely in Appendix H, oncologic outcomes include late effects (symptoms) **identified** and **addressed**, receipt of head and neck surveillance and appropriate follow-up (e.g. dental exam for those who underwent radiation therapy). Non-oncologic outcomes include receipt of recommended routine preventive care (e.g., cancer screening, tobacco cessation).

**11.3.1 Oncologic outcomes.** We will only investigate late effects that we assess in HN-STAR. (If usability testing identifies additional late effects we did not target in our Survivor Self-Assessment, we will add them to the Survivor Self-Assessment for Aim 1: Part 2 and include them in Appendix H.) For each late effect, we will consider it identified if it was mentioned in a clinic note, and we will consider it addressed if there was a referral,

recommendation, education, or explicit acknowledgement of inaction. (Inaction may be appropriate, because in some cases, when symptoms are persistent and intractable, no intervention may be recommended.) For each patient, we will first count the number of late effects identified. We will then calculate the proportion of identified late effects that are addressed.

We will use descriptive statistics to report each element of oncologic care listed in Appendix H (i.e. smoking cessation, dental exam, blood work for thyroid studies, endoscopic exam, and head and neck physical exam). Each patient may not require every element of follow-up, depending on their primary tumor site or treatment received. We will use the number of recommended elements of care as the denominator, and we will calculate the proportion of these elements that are performed.

**11.3.2 Non-oncologic outcomes.** The non-oncologic outcomes in HN-STAR are collected only once. They include cancer screening, vaccination, and other preventive care elements that are explicitly collected in the Survivor Self-Assessment. Only some of these elements will be recommended for each patient, depending on their age, sex, and behaviors. We will calculate the proportion of recommended elements of non-oncologic care that are performed per patient. In addition, for each element of non-oncologic care, we will calculate the proportion of patients who receive it as recommended.

Findings from Aim 2 will inform whether these metrics can be collected from the EMR and HN-STAR. In addition, they will inform the statistical analysis for the future trial. For oncologic metrics only (Section 9.0, Figure 4), we will calculate the difference before HN-STAR use and after. Differences in oncologic metrics will be used in the power calculation for the proposed randomized trial. Non-oncologic metrics will be reported descriptively to inform the feasibility of collecting these data from self-report.

**11.4 Adaptation of and advance of HN-STAR.** If HN-STAR is deemed feasible for further effectiveness testing, we will use our findings to adapt the content of HN-STAR. We will then advance HN-STAR to a randomized clinical trial to assess its effectiveness in improving the health outcomes assessed in Aim 2.

